4.5.5 Follow Up Period (Day 4 -27)

The subject will have a daily follow up collecting all of the below assessments. If the patient reaches an aPTT value of 70-90 seconds, subsequently daily aPTT values will be record until discharge or Day 28.

- Neurological Exam

- Vitals

- Laboratory Samples (Standard of care)

- Respiratory Status / Ventilator Settings

- Ordinal Scale Assessment

- Imaging (Standard of Care)

- Concomitant medication review (excluding “prn” or “as needed” medications)

4.5.6 End of Study (Day 28)

The following assessments will be collected at the final End of Study timepoint if the patient is still admitted:

- Neurological Exam

- Vitals

- Laboratory Samples (Standard of care)

Tenecteplase–Icahn School of Medicine at Mount Sinai
Protocol ML42492

20

Thromboelastograms (when available according to standard practice)

- Respiratory Status / Ventilator Settings
- Imaging (Standard of Care)
- Concomitant medication review (excluding “prn” or “as needed” medications)

The ordinal scale assessment will be completed at day 28 regardless of whether the patient is admitted or discharged.

4.6 TREATMENT, PATIENT, AND STUDY DISCONTINUATION

Patients must permanently discontinue study treatment (tenecteplase or placebo) if they experience any of the following:

- Intolerable toxicity related to study treatment, including development of an immune-mediated adverse event determined by the investigator to be unacceptable given the individual patient’s potential response to therapy and severity of the event
- Any medical condition that may jeopardize the patient’s safety if he or she continues study treatment
- Investigator determines it is in the best interest of the patient
- Pregnancy
- Anaphylaxis or other severe hypersensitivity reaction
- Loss of clinical benefit as determined by the investigator after an integrated assessment of clinical status (e.g., symptomatic deterioration such as pain secondary to disease) (see Section 3.1.1 for details)

The primary reason for study treatment discontinuation should be documented in the patient’s medical records. Patients who discontinue study treatment prematurely will not be replaced.

4.6.1 Patient Discontinuation from Study

Patients have the right to voluntarily withdraw from the study at any time for any reason. In addition, the investigator has the right to withdraw a patient from the study at any time. Reasons for withdrawal from the study may include, but are not limited to, the following:

- Withdrawal of consent
- Study termination or site closure
- Patient non-compliance, defined as failure to comply with protocol requirements as determined by the Investigator

Every effort should be made to obtain information on patients who withdraw from the study. The primary reason for withdrawal from the study should be documented in the patient’s medical records. If a patient requests to be withdrawn from the study, this request must be documented in the source documents and signed by the investigator. Patients who withdraw from the study will not be replaced.

If a patient withdraws from the study, the study staff may use a public information source (e.g., county records) to obtain information about survival status.

4.6.2 Study Discontinuation

The Investigator has the right to terminate this study at any time. Reasons for terminating the study may include, but are not limited to, the following:

- The incidence or severity of adverse events in this or other studies indicates a potential health hazard to patients
- Patient enrollment is unsatisfactory

5. ASSESSMENT OF SAFETY

5.1 SAFETY PLAN

The safety plan for patients in this study is based on clinical experience with tenecteplase in completed and ongoing studies. The anticipated important safety risks for tenecteplase are outlined below. Please refer to the Tenecteplase Investigator's Brochure for a complete summary of safety information.

Several measures will be taken to ensure the safety of patients participating in this study. Eligibility criteria have been designed to exclude patients at higher risk for toxicities. Patients will undergo safety monitoring during the study, including assessment of the nature, frequency, and severity of adverse events. In addition, guidelines for managing adverse events are provided below.

Measures will be taken to ensure the safety of patients participating in this study, including the use of stringent inclusion and exclusion criteria and close monitoring of patients during the study. Administration of tenecteplase, and the placebo, will be performed in a monitored setting in which there is immediate access to trained personnel and adequate equipment and medicine to manage potentially serious reactions. Refer to Sections 5.2–5.6 for details on safety reporting (e.g., adverse events, pregnancies) during the study.

5.1.1 Stopping Rules

In the case of any Mortality during the 28 day follow up period, enrollment will be halted and DSMC/CEC review will be performed within 72 hrs of notification. The DSMC will then issue a report back to the study PI regarding their recommendation as to re-opening the study or permanently closing the study.

Should there occur, at any time during the study, a difference between the control and treatment cohorts of >2 intracerebral hemorrhages then the study will be halted. Per protocol, the DSMC/CEC will review all ICH's (SAE's). Following each of these individual case reviews (after analysis/interpretation locked), the DSMC/CEC statistician (who is unblinded, not the study statistician, who will remain blinded) will provide summary data on the ICH's according to cohort. If there is a greater than 2 ICH differential then the study will be halted. Additionally, the DSMC/CEC will be reviewing all enrollments, with summary statistics for each cohort (provided by the DSMC/CEC statistician) after each 15 patients are enrolled. They are empowered to halt study enrollment at each of these review points should there be safety concerns. After each of these planned DSMC/CEC reviews the DSMC/CEC will generate a formal report to provide to the study PI.

Tenecteplase–Icahn School of Medicine at Mount Sinai
Protocol ML42492

22

5.1.2 Risks Associated with Tenecteplase

Standard management of myocardial infarction should be implemented concomitantly with tenecteplase treatment.

Arterial and venous punctures should be minimized. Non-compressible arterial puncture must be avoided, and internal jugular and subclavian venous punctures should be avoided to minimize bleeding from the non-compressible sites. In the event of serious bleeding, heparin and antiplatelet agents should be discontinued immediately and treated appropriately. Heparin effects can be reversed by protamine.

5.1.2.1 Bleeding

The most common complication encountered during tenecteplase therapy is bleeding. This may be either superficial from punctures or damaged blood vessels or internal bleeding at any site or body cavity. Bleeding may result in life-threatening situations, permanent disability, or death.

- The incidence of ICH, especially sICH, in patients with AIS is higher in alteplase-treated patients than placebo-treated patients in published studies (for detailed information, see the alteplase USPI).

The type of bleeding associated with thrombolytic therapy can be divided into two broad categories:

- Internal bleeding, involving intracranial and retroperitoneal sites, or the gastrointestinal, genitourinary, or respiratory tracts
- Superficial or surface bleeding, observed mainly at vascular puncture and access sites (e.g., venous cutdowns, arterial punctures) or sites of recent surgical intervention

Management of Bleeding

Patients will be excluded for the presence of conditions related to risks of bleeding (as outlined in Section 4.1.2 Exclusion Criteria).

Should an arterial puncture be necessary during the first few hours following tenecteplase therapy, the use of an upper extremity vessel that is accessible to manual compression is preferable. Pressure should be applied for at least 30 minutes, a pressure dressing applied, and the puncture site checked frequently for evidence of bleeding.

Each patient being considered for therapy with tenecteplase should be carefully evaluated and anticipated benefits weighed against potential risks associated with therapy.

Guidelines for management of patients who develop bleeding are provided in [Table 1](#).

In addition, any ICH events (symptomatic and/or asymptomatic), if not already reported as an SAE by the investigator, are considered non-serious adverse events of special interest for this study (Section [5.2.3](#)) and should be reported and submitted to the Sponsor (Section [5.4](#)).

5.1.2.2 Arrhythmias

Coronary thrombolysis may result in arrhythmias associated with reperfusion. These arrhythmias (such as sinus bradycardia, accelerated idioventricular rhythm, ventricular

Tenecteplase–Icahn School of Medicine at Mount Sinai
Protocol ML42492

23

premature depolarizations, ventricular tachycardia, etc.) are not different from those often seen in the ordinary course of AMI and may be managed with standard anti-arrhythmic measures. It is recommended that anti-arrhythmic therapy for bradycardia and ventricular irritability be available when tenecteplase is administered.

5.1.2.3 Thromboembolism

The use of thrombolytics can increase the risk of thromboembolic events in patients with high likelihood of left heart thrombus, such as patients with mitral stenosis or atrial fibrillation.

5.1.2.4 Cholesterol Embolization

Cholesterol embolism has been reported rarely in patients treated with all types of thrombolytic agents; the true incidence is unknown. This serious condition, which can be lethal, is also associated with invasive vascular procedures (e.g., cardiac catheterization, angiography, vascular surgery) and/or anticoagulant therapy. Clinical features of cholesterol embolism may include livedo reticularis, "purple toe" syndrome, acute renal failure, gangrenous digits, hypertension, pancreatitis, myocardial infarction, cerebral infarction, spinal cord infarction, retinal artery occlusion, bowel infarction, and rhabdomyolysis.

5.1.2.5 Use with Percutaneous Coronary Intervention

In patients with ST segment elevation myocardial infarction, physicians should choose either thrombolysis or PCI as the primary treatment strategy for reperfusion. Rescue PCI if medically appropriate or subsequent elective PCI may be performed after administration of thrombolytic therapies; however, the optimal use of adjunctive antithrombotic and antiplatelet therapies in this setting is unknown.

5.1.3 Precautions

Standard management of acute ischemic stroke should be implemented concomitantly with tenecteplase treatment. Arterial and venous punctures should be minimized. Noncompressible arterial puncture must be avoided and internal jugular and subclavian venous punctures should be avoided to minimize bleeding from the noncompressible sites. In the event of serious bleeding, heparin and antiplatelet agents should be discontinued immediately. Heparin effects can be reversed by protamine.

5.1.3.1 Re-administration

Re-administration of plasminogen activators, including tenecteplase, to patients who have received prior plasminogen activator therapy has not been systematically studied. Three of 487 patients tested for antibody formation to tenecteplase had a positive antibody titer at 30 days. The data reflect the percentage of patients whose test results were considered positive for antibodies to tenecteplase in a radioimmunoprecipitation assay and are highly dependent on the sensitivity and specificity of the assay. Additionally, the observed incidence of antibody positivity in an assay may be influenced by several factors including sample handling, concomitant medications, and underlying disease. For these reasons, comparison of the incidence of antibodies to tenecteplase with the incidence of antibodies to other products may be misleading. Although sustained antibody formation in patients receiving one dose of tenecteplase has not been documented, re-administration should be undertaken with caution.

5.1.3.2 Hypersensitivity

Hypersensitivity, including urticarial/anaphylactic reactions, have rarely (<1%) been reported after administration of tenecteplase (e.g., anaphylaxis, angioedema, laryngeal edema, rash, and Tenecteplase-Icahn School of Medicine at Mount Sinai Protocol ML42492

urticaria). Monitor patients treated with tenecteplase during and for several hours after infusion. If symptoms of hypersensitivity occur, appropriate therapy should be initiated.

5.1.3.3 Drug Interactions

Formal interaction studies of tenecteplase with other drugs have not been performed. Patients studied in clinical trials of tenecteplase were routinely treated with heparin and aspirin. Anticoagulants (such as direct oral anticoagulants, heparin and vitamin K antagonists) and drugs that alter platelet function (such as acetylsalicylic acid, dipyridamole, and GP IIb/IIIa inhibitors) may increase the risk of bleeding if administered prior to, during, or after tenecteplase therapy.

5.1.3.4 Drug/Laboratory Test Interactions

During tenecteplase therapy, results of coagulation tests and/or measures of fibrinolytic activity may be unreliable unless specific precautions are taken to prevent in vitro artifacts. Tenecteplase is an enzyme that, when present in blood in pharmacologic concentrations, remains active under in vitro conditions. This can lead to degradation of fibrinogen in blood samples removed for analysis.

5.1.4 Management of Patients Who Experience Adverse Events

5.1.4.1 Management Guidelines

Guidelines for management of specific adverse events are outlined in Table 1.

Table 1 Guidelines for Management of Patients Who Experience Bleeding

Event	Action to Be Taken
Bleeding	
• In the event of serious bleeding, heparin and antiplatelet agents should be discontinued immediately and treated appropriately. Heparin effects can be reversed by protamine.• Intramuscular injections and nonessential handling of the patient should be avoided for the first few hours following treatment with tenecteplase.• Venipunctures should be performed and monitored carefully.• Should an arterial puncture be necessary during the first few hours following tenecteplase therapy, it is preferable to use an upper extremity vessel that is accessible to manual compression. Pressure should be applied for at least 30 minutes, a pressure dressing applied, and the puncture site checked frequently for evidence of bleeding.

Refer to Sections 5.2–5.6 for details on safety reporting (e.g., adverse events, pregnancies) for this study.

Tenecteplase–Icahn School of Medicine at Mount Sinai
Protocol ML42492

25

5.2 SAFETY PARAMETERS AND DEFINITIONS

Safety assessments will consist of monitoring and reporting adverse events and serious adverse events per protocol. This includes all events of death and any study-specific issue of concern.

5.2.1 Adverse Events

An AE is any unfavorable and unintended sign, symptom, or disease temporally associated with the use of an investigational medicinal product (IMP) or other protocol-imposed intervention, regardless of attribution.

This includes the following:

- AEs not previously observed in the patient that emerge during the protocol-specified AE reporting period, including signs or symptoms associated with AMI that were not present prior to the AE reporting period.
- Complications that occur as a result of protocol-mandated interventions (e.g., invasive procedures such as cardiac catheterizations).
- If applicable, AEs that occur prior to assignment of study treatment associated with medication washout, no treatment run-in, or other protocol-mandated intervention.
- Pre-Existing medical conditions (other than the condition being studied) judged by the investigator to have worsened in severity or frequency or changed in character during the protocol-specified AE reporting period.

5.2.2 Serious Adverse Events

An AE should be classified as an SAE if the following criteria are met:

- It results in death (i.e., the AE actually causes or leads to death).
- It is life threatening (i.e., the AE, in the view of the investigator, places the patient at immediate risk of death. It does not include an AE that, had it occurred in a more severe form, might have caused death.).
- It requires or prolongs inpatient hospitalization.
- It results in persistent or significant disability/incapacity (i.e., the AE results in substantial disruption of the patient's ability to conduct normal life functions).
- It results in a congenital anomaly/birth defect in a neonate/infant born to a mother exposed to the IMP.
- It is considered a significant medical event by the investigator based on medical judgment (e.g., may jeopardize the patient or may require medical/surgical intervention to prevent one of the outcomes listed above).

5.2.3 Adverse Events of Special Interest

Non-serious adverse events of special interest are required to be reported by the investigator to the Sponsor immediately (i.e., no more than 24 hours after learning of the event). Non-serious adverse events of special interest for this study are as follows:

- Any ICH events (symptomatic and/or asymptomatic), if not already reported as an SAE
- The non-drug specific AESIs:

Tenecteplase–Icahn School of Medicine at Mount Sinai
Protocol ML42492

- Cases of potential drug-induced liver injury that include an elevated ALT or AST in combination with either an elevated bilirubin or clinical jaundice, as defined by Hy's Law.
- Suspected transmission of an infectious agent by the study drug, as defined below
 - Any organism, virus, or infectious particle (e.g., prion protein transmitting transmissible spongiform encephalopathy), pathogenic or non-pathogenic, is considered an infectious agent. A transmission of an infectious agent may be suspected from clinical symptoms or laboratory findings that indicate an infection in a patient exposed to a medicinal product. This term applies only when a contamination of the study drug is suspected.

5.3 METHODS AND TIMING FOR ASSESSING AND RECORDING SAFETY VARIABLES

The investigator is responsible for ensuring that all AEs and SAEs that are observed or reported during the study, are collected and reported to the FDA, appropriate IRB(s), and Genentech, Inc. in accordance with CFR 312.32 (IND Safety Reports).

5.3.1 Adverse Event Reporting Period

The study period during which all AEs and SAEs must be reported begins after informed consent is obtained and initiation of any study procedures and ends 28 days following the last administration of study treatment or study discontinuation/termination, whichever is earlier. After this period, investigators should only report SAEs that are attributed to prior study treatment.

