5.4.4.2 Post-Study Adverse Events

The investigator should expeditiously report any SAE occurring after a patient has completed or discontinued study participation if attributed to prior tenecteplase exposure. If the investigator should become aware of the development of cancer or a congenital anomaly in a subsequently conceived offspring of a female patient who participated in the study, this should be reported as an SAE.

Case Transmission Verification will be performed by both parties during this period to ensure successful transmission of Single case reports.

CASE TRANSMISSION VERIFICATION OF SINGLE CASE REPORTS

The Sponsor agrees to conduct the Case Transmission verification to ensure that all single case reports have been adequately received by Genentech via [name] emailing Genentech a Quarterly line-listing documenting single case reports sent by [name] to Genentech in the preceding time period.

Tenecteplase–Icahn School of Medicine at Mount Sinai
Protocol ML42492

31

The periodic line-listing will be exchanged within seven (7) calendar days of the end of the agreed time period. Confirmation of receipt should be received within the time period mutually agreed upon.

If discrepancies are identified, the Sponsor and Genentech will cooperate in resolving the discrepancies. The responsible individuals for each party shall handle the matter on a case-by-case basis until satisfactory resolution. The sponsor shall receive reconciliation guidance documents within the 'Activation Package'.

Following Case Transmission Verification, single case reports which have not been received by Genentech shall be forwarded by [name] to Genentech within five (5) calendar days from request by Genentech.

At the end of the study, a final cumulative Case Transmission Verification report will be sent to Genentech.

AEs of Special Interest (AESIs)

AESIs are a subset of Events to Monitor (EtMs) of scientific and medical concern specific to the product, for which ongoing monitoring and rapid communication by the Investigator to the Sponsor is required. Such an event might require further investigation in order to characterize and understand it. Depending on the nature of the event, rapid communication by the trial Sponsor to other parties (e.g., Regulatory Authorities) may also be warranted.

Adverse events of special interest for this study include the following:

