6.3 PRIMARY SAFETY VARIABLE

Data will be analyzed according to the occurrence, at any time between tenecteplase administration and day 28, of intracranial hemorrhage or major bleeding event (defined above). Outcome will be the proportion of patients who have suffered no intracranial hemorrhage or major bleeding event. Those patients who have suffered an intracranial hemorrhage or major bleeding event will be assessed as failures for the purposes of the safety analysis.

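### All-AE/SAE reporting can close at study termination before day 28, so patients already given the single bolus may lose systematic safety follow-up

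*Combined protocol and SAP*

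**What the plan says.** Section 5.3.1 opens the AE/SAE reporting period after consent and states that it "ends 28 days following the last administration of study treatment or study discontinuation/termination, whichever is earlier". It continues: "After this period, investigators should only report SAEs that are attributed to prior study treatment". Section 5.4.4.2 repeats the residual duty: "The investigator should expeditiously report any SAE occurring after a patient has completed or discontinued study participation if attributed to prior tenecteplase exposure".

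Section 4.6.1 gives "Study termination or site closure" among the reasons for withdrawing a patient. It adds "Every effort should be made to obtain information on patients who withdraw from the study" and lets staff look up survival status in public records.

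Section 4.6.2 foresees termination for safety: "The incidence or severity of adverse events in this or other studies indicates a potential health hazard to patients". Under Section 5.1.1, a death halts enrollment pending committee review, which may lead to re-opening or to permanent closure. A difference of more than 2 intracerebral hemorrhages between cohorts halts the study, but what a halt means is not defined.

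Section 6.3 defines the primary safety variable from administration to day 28: "Those patients who have suffered an intracranial hemorrhage or major bleeding event will be assessed as failures for the purposes of the safety analysis". It gives no rule for incomplete follow-up. Section 2.3 gives the same outcome a 72-hour window from randomization. Appendix 1, note k, requires AEs to be recorded from consent to the end-of-study visit and mentions no termination cut-off.

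**The concern.** Section 3.3.1 limits each patient to one dose of tenecteplase. Ending the study therefore does not reduce the exposure of anyone already dosed; it only ends the observation of that exposure.

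The cut-off applies in the situation where complete bleeding data matter most. If the study is permanently closed for a bleeding signal, the patients dosed most recently have the shortest observation, and after escalation those on active drug are at the higher dose level. The data that would describe the signal could be thinned by the decision that the signal prompted.

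The day-28 variable in Section 6.3 and 28-day mortality in Section 2.3 both need follow-up that Section 5.3.1 permits to stop.

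**Working it through.** **The plan's own safety figures.** Section 6.1 gives the chance of at least one event in 20 patients as at least 45% at a true rate of 3% and at least 70% at 6%. Both reproduce:

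- 1 − (1 − 0.03)^20 = 45.6%
- 1 − (1 − 0.06)^20 = 71.0%

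The point does not dispute these figures. They do presuppose that all 20 patients are observed for the whole outcome window.

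**What must still be reported after the cut-off.** Set Section 6.3 against the residual duty in Sections 5.3.1 and 5.4.4.2.

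- *Serious bleed attributed to tenecteplase.* It counts in 6.3 and stays reportable.
- *Intracranial hemorrhage not reported as an SAE, including asymptomatic.* Sections 5.1.2.1 and 5.2.3 class it as a non-serious event of special interest. Section 6.3 counts intracranial hemorrhage without requiring symptoms. The residual duty covers only SAEs, so this event falls outside it.
- *Serious bleed judged unrelated to tenecteplase.* It counts in 6.3, which has no attribution condition. Section 5.3.2 allows a concomitant medication as the alternative cause, and the protocol combines study drug with heparin (Section 4.3). A bleed attributed to heparin need not be reported.
- *Other unrelated SAEs.* They need not be reported after the cut-off, although Section 5.4.1 has the committee review related and unrelated SAEs alike.

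**Patients inside the window at a termination during accrual.** Inputs: 60 patients (Section 4.1); first enrollment 15 June and last 15 November 2020 (Section 3.2), which is 153 days; 2:1 allocation (Section 3.1). Uniform accrual is an assumption.

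Patients in window = (60 / accrual days) × window length.

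- 28-day window: 60/153 × 28 = 11.0, of whom 2/3 = 7.3 on tenecteplase.
- As a share of the planned trial: 11/60 = 18%.
- 72-hour window: 60/153 × 3 = 1.2.
- Accrual over an assumed 100 days: 60/100 × 28 = 16.8, of whom 11.2 on tenecteplase.
- Accrual over an assumed 300 days: 60/300 × 28 = 5.6, of whom 3.7 on tenecteplase.

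If every dosed patient stayed under reporting to day 28, the number cut short by a termination would be 0.

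**The case against.** Several points on the other side have force.

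*Reporting does not stop altogether.* A reader might infer that a serious day-5 hemorrhage would vanish. That is too strong. Table 3 treats an event as related unless the exclusion criteria are met, and bleeding is a known effect of the drug, so such an event would normally remain reportable. This stands. The loss is in non-serious events, events judged unrelated, and systematic ascertainment.

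*A halt is not a termination.* A reader might infer that any safety stop cuts off follow-up. For deaths, Section 5.1.1 speaks of halting enrollment, with re-opening possible, and Section 5.4.1 also refers to halting enrollment. This stands. Only a permanent termination clearly triggers the cut-off, and whether a halt under the hemorrhage rule is one is left open.

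*Withdrawn patients are not abandoned.* Section 4.6.1 asks for every effort to obtain information. That is a mitigation, but it has no schedule, and the survival check is optional and yields no bleeding data.

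*Section 5.3.1 can be read differently*, as 28 days after the earlier of the last dose or discontinuation. With one bolus, that always means 28 days after dosing, and the closing qualifier would then do no work. The natural reading is therefore the one used here, but the wording is ambiguous.

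*Non-compliance.* Section 4.6.1 also lists "Patient non-compliance, defined as failure to comply with protocol requirements as determined by the Investigator". A reader might infer that a patient whose heparin is stopped for bleeding could be withdrawn on this ground and the bleed lost. The documents do not support that. Sections 5.1.2 and 5.1.3 and Table 1 themselves direct that heparin be discontinued in serious bleeding, and that bleed would already be on record.

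**Conclusion.** The point holds for a permanent termination. Sections 5.3.1 and 4.6.1 allow collection of all AEs and SAEs to end before day 28 in patients already dosed, and nothing elsewhere restores it. This is a stated rule that conflicts with Section 6.3 and with note k, so it is more than a missing detail.

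The size is about 11 patients in the 28-day window, about 7 of them on tenecteplase, as an average under assumed uniform accrual at the planned pace. It should not be read as an upper limit: the count is about 17 if accrual takes 100 days and about 6 if it takes 300. Cohort reviews and halts after deaths make uniform accrual unlikely. On the 72-hour window of Section 2.3 only about 1 patient is affected, so the size also depends on which of the two windows governs.

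A reader might infer that Section 6.3 counts patients with truncated follow-up as safe. It does not say so; it is silent. The risk is that, with only known bleeds defined as failures and no rule for incomplete follow-up, such patients end up event-free by default. The carry-forward rule in Section 6.2 is stated for efficacy only.

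**What to change.** - **Section 5.3.1:** end the reporting period at 28 days after study drug for every dosed patient, including after study termination or site closure, unless the patient withdraws consent to follow-up.
- **Sections 4.6.1 and 5.1.1 and Appendix 1, note k:** align with this. State that a halt or termination, whatever it means for enrollment and dosing, does not end follow-up of patients already dosed, and say whether a halt under the hemorrhage rule counts as a termination.
- **Section 6.3:** report events together with the number actually followed to day 28, or analyze time to event with censoring at last contact, so that truncated patients are not counted as event-free. Reconcile the window with Section 2.3.

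The cost is wording, plus at most 28 days of follow-up that Appendix 1 already schedules. The database would close up to four weeks later after an early termination. The consent pages are not available for review, so the sponsor should check that the consent form covers follow-up after termination.
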